## 1. SYNOPSIS

Study Title	Design, implementation and assessment of a comprehensive community neonatal health package utilising medical and social interventions	
Internal ref. no.	N/A	
Study Design	Cluster randomised control trial	
Study Participants	The population of Preah Vihear (PVH) province, Cambodia	
Planned Sample Size	
 
293 villages with 586 Village Health Support Group Workers (VHSG)
 
26,500 children born in Preah Vihear over the study period and their parents (5,300 deliveries a year)
 
306 health centre nurses and midwives from 28 health centres and 17 health posts in Preah Vihear
 
30 nurses, 27 midwives and 18 doctors from Preah Vihear Referral Hospital
 
	
Planned Study Period	5 years	
	Objectives	Outcome Measures
Primary	The design, implementation and assessment of a comprehensive community neonatal health package utilising medical and social interventions	A comprehensive community neonatal health package utilising medical and social interventions
Secondary	Reduction of perinatal mortality in PVH province, Cambodia	A one third reduction in perinatal mortality in PVH province, Cambodia
Tertiary	To describe the characteristics of neonates, born in PVH province, Cambodia over a five-year time period	A document that describes the characteristics of neonates, born in PVH province, Cambodia over a five-year time period
	To develop a tool to undertake a full review of neonatal services and capabilities in PVH province, Cambodia	A user-friendly tool to assess neonatal healthcare services A report detailing neonatal services and capabilities in PVH province, Cambodia
	Design a fully comprehensive neonatal healthcare training and implementation package adapted to local need	A locally appropriate neonatal healthcare training and implementation package
	Establish regular VHSG meetings to address areas of concern for the local community with respect to childbirth and the neonatal period	Frequency and attendance rate of participants at the programmes VHSG group meetings

	
With the Kingdom of Cambodia, Ministry of Health and the Provincial Health Director of PVH province develop a programme blueprint and implementation strategy for introduction of the developed programme into other locations within Cambodia
	
A programme and implementation plan for the reduction of neonatal mortality that can be used throughout Cambodia

	
To calculate the cost-effectiveness of a neonatal community health programme and the resulting changes in care, as compared to the existing care given in the region
	
A cost effectiveness analysis

## 2. ABBREVIATIONS

AHC	Angkor Hospital for Children
CI	Chief Investigator
COMRU	Cambodia Oxford Medical Research Unit
CRF	Case Report Form
GCP	Good Clinical Practice
HC	Health Centre
HP	Health Post
KAP	Knowledge, Attitudes and Practice
KAPES	Knowledge, Attitudes, Practice, Equipment and Staff
NMR	Neonatal mortality rate
OxTREC	Oxford Tropical Research Ethics Committee
PAR	Participatory Action Research
PI	Principal Investigator
PIS	Participant Information Sheet
PVH	Preah Vihear
SBLP	Saving Babies Lives Programme
SBLT	Saving Babies Lives Team
VHSG	Village Health Support Group

### **3. BACKGROUND AND RATIONALE**

Globally the proportion of childhood deaths that occur in the neonatal period is increasing [1]. Since 1990 there has been a 47% reduction in deaths in children less than five years of age [2]. However, this rate of reduction has not been seen in infants four weeks of age or younger (neonates). It is estimated that 2.9 million neonates die each year, with one million of these occurring on the first day of life [3]. Neonatal mortality now makes up 44% of all deaths in children younger than five years [3]. The reasons why the fall in neonatal mortality has not mirrored that seen in children mortality, is complex and one that is not well explored in the literature.

Cambodia has met most targets of the 4th and 5th Millennium Development Goals, reducing child mortality and improving maternal health by investing in health systems [4, 5]. However, the Sustainable Development Goals call for further improvements and Cambodia continues to fall behind its neighbouring countries in reducing neonatal mortality [6].

One proposed explanation is that interventions that have been successfully employed to reduce childhood death do not reach the community and it is in the community where most neonates die [7, 8]. Another pervasive perceived barrier to providing neonatal care, particularly in remote and rural areas, is the misconception that neonatal care is difficult and expensive [9].

During the neonatal period, perhaps more than at any other time, there are deep rooted health practices and beliefs. These differ in different communities but often share common themes. Hot bed use, food avoidance in the mother postpartum, discarding colostrum and application of various substances to the umbilical cord (such as cow dung, petrol and ash) are examples of widely held practices [10-12]. Many of these practices are potentially harmful to the neonate and need to be addressed in the communities where they occur by community engagement and education.

#### **Community**

Many health problems are rooted in powerlessness. Health education that involves community involvement: dialogue and problem solving, rather than just message giving, is more empowering. Addressing social needs and empowering communities to make decisions about health care needs allows for the design of programmes that account for local practices and beliefs [13, 14]. In participatory action research (PAR) communities identify and prioritise problems, develop action plans, implement these plans and assess them [15-18]. Community assessment of health problems and barriers increases the awareness of those problems; it has been shown to increase social support and participation in problem solving [13]. PAR uses facilitation rather than teaching to increase knowledge in community groups.

#### **Health Care facilities**

Up to two-thirds of neonatal deaths could be prevented if neonates were given proper care during and immediately after birth, because the majority of neonatal deaths occur around the time of delivery [19]. Training primary level health care workers to deal with emergency situations that occur around the time of delivery, such as ante-partum and post-partum haemorrhage, umbilical cord prolapse and shoulder dystocia, has been shown to decrease maternal mortality and neonatal mortality [20]. Similarly, a model for neonatal care in low-resource settings, special baby care areas, has been proven to significantly reduce neonatal mortality over a period of a few years [9].

It is reported that 79% of deliveries in Cambodia occur in healthcare facilities [21]. The majority of these will occur at primary healthcare facilities (health centres (HC) or health Posts (HP)). Babies born in HCs or

HPs who require further care are referred to the referral hospital. The majority of referral hospitals in Cambodia do not have the resources or skills to effectively deal with neonatal complications for babies born either in health centres or in their on-site maternity wards.

The Saving Babies Lives Programme will be developed in partnership with the Kingdom of Cambodia Ministry of Health (MoH). The programme will be approved by the MoH and a memorandum of understanding signed with the provincial health director of Preah Vihear (PVH) province. The major objective of this project is to develop a programme blueprint and implementation strategy for introduction of the developed programme into other locations within Cambodia. Data will be collected and used to assess the impact of the programme, its perceived facilitators and barriers and its successes and failures. This information will be used to iterate the programme content and structure in order to improve it.

### **3.1. Research Question**

The central hypothesis of this study is that a neonatal healthcare programme that has a significant impact on neonatal mortality and which spans the healthcare journey from village to referral hospital can be developed and implemented in low resource rural setting

#### **Aim of the study**

The design, implementation and assessment of a comprehensive community neonatal health package utilising medical and social interventions

### **3.2. Intervention**

The study has four components

1. Design and implementation of a locally appropriate comprehensive neonatal healthcare package – Saving Babies Lives Programme (SBLP)
2. Establishment of baby health meetings for VHSGs
3. Measurement of perinatal mortality in PVH province
4. Economic evaluation of the programme and its implementation

#### **Saving Babies Lives Programme**

A comprehensive, contextual and adaptive neonatal healthcare package will be developed using the Kingdom of Cambodia national guidelines on neonatal and maternal health, WHO maternal and child health guidelines and results from the pre-implementation assessment [24-26]. Course-based training will be combined with continuous in-situ mentoring to support doctors, nurses and midwives and other health worker cadres in order to improve their practical daily skills in emergency and clinical neonatal care. Essential equipment will be identified and included in the package. The neonatal healthcare package will be developed by the Saving Babies Lives team which consists of experienced nursing and medical staff working at the Angkor Hospital for Children (AHC), Cambodia. AHC is a non-governmental teaching hospital that has been in operation since 1999. Each year it provides approximately 180,000 free treatments to neonates and children and has a dedicated neonatal care programme.

A neonatal healthcare assessment tool will be developed that is quantitative and qualitative in nature. It will be based on the KAP survey method of analysing Knowledge, Attitudes and Practice. KAP involves a representative survey on a specific topic, of a particular population, by using predefined questions in standardised questionnaires, to produce data which may be quantitative, qualitative, or a mixture of the

[figure not shown]
two [27, 28]. In addition, two further domains will be added, equipment and staffing, leading to a “KAPES” model of assessment. Before the neonatal healthcare package is introduced into a HC or HP the KAPES assessment will be carried out. It will also be performed after the initial training period and then annually until the end of the study. The information gathered using this tool will further inform the content of the neonatal health care package.

### VHSG Baby Health Meetings

Baby Health meetings (BHM) will be conducted at each HC. Each BHM will be attended by two VHSG from each of the villages served by the HC. The purpose of the BHM is to identify problems and concerns around neonatal health care in their own village. Monthly meetings will take place at the HC in order for the group to discuss problems, attempt to arrive at solutions, and share learning. These meetings will be facilitated by the SBL team who will use a Participatory Action Research (PAR) methodology to:

1. Identify problems with provision of, and barriers to seeking, neonatal health care
2. Develop interventions to improve care
3. Implement these interventions
4. Assess the group’s perception of the effectiveness of interventions (Figure 1).

Specific questions and prompts will be devised by the SBLT prior to the meeting and will be based on experiences gained from previous meetings. The use of storytelling will be used to simulate discussion [22].

**Figure 1. Overview of the baby health meetings**

### ***Set-up***

The BHM will be conducted in the HCs chosen to be in the intervention group. Both prior to the meeting and after it refreshments will be served. The group will decide whether they want to sit on chairs or the floor. At the start of the first meeting ground rules will be discussed and agreed upon; these will be written in Khmer and displayed at each subsequent meeting. Flip charts, post it notes and pens will be available during each session to help clarify points and to reach consensus about topics. These charts will be photographed at the end of each meeting. All participants will receive their travel costs, calculated by distance travelled and at a fixed rate and paid at the end of the meeting.

### ***Conducting the Meetings***

The meetings will be conducted in Khmer by one of the SBLT. A focus group discussion like method will be used, with the SBLT member encouraging discussion and interaction in the group. A meeting topic guide will be used for each meeting (Appendix 1. Baby Health Meeting topic guide

### ***Recording the Meetings***

**An observer will be present to take notes on nonverbal communication and interactions using a meeting observation form (Appendix 1. Baby Health Meeting topic guide**

## Baby Health Meetings for Saving Babies Lives

### Meeting topic guide

HC code: |\_\_\_\_\_|\_\_\_\_\_|\_\_\_\_\_|\_\_\_\_\_| Facilitator Initials: |\_\_\_\_\_|\_\_\_\_\_|\_\_\_\_\_| Note-taker Initials: |\_\_\_\_\_|\_\_\_\_\_|\_\_\_\_|

Date: |\_\_\_\_\_|\_\_\_\_\_|\_\_\_\_\_|\_\_\_\_\_|\_\_\_\_\_|\_\_\_\_\_|

Meeting number: |\_\_\_\_\_|\_\_\_\_|

### Introduction

I am \_\_\_\_\_ from \_\_\_\_\_ (Facilitator)

I am \_\_\_\_\_ from \_\_\_\_\_ (note-taker)

- ⇒ Ask group to introduce themselves using first names
- ⇒ Todays topic for discussion (check meeting time table and use specific guide)
- ⇒ Aims of the discussion and expected duration (1 hour)
- ⇒ Remind the group of the ground rules
- ⇒ Any questions
- ⇒ Check position of the tape recorder
- ⇒ Check for everyone's consent to participate and be recorded
- ⇒ Refreshments will be served before and after the discussion
- ⇒ Travel reimbursement will be given after the meeting

Questions	Prompts

Appendix 2). Each participant will be given an ID number and these will be used so that the note taker can draw a map of where people were sitting and attribute contributions to specific people.

### **Contact Summary Forms**

At the end of each meeting the SBLT will meet and complete a contact summary form, documenting the meeting process (Appendix ).

### **Perinatal Mortality**

The expected outcome of the SBLP is a reduction in perinatal mortality (PMR). In order to assess the effectiveness of the SBLP an accurate measure of PMR is needed. Although births and deaths are required to be registered in Cambodia, often the births and deaths of young infants, particularly those born at home, are not registered. To accurately determine the perinatal mortality rate (PMR) in PVH province, government village health support groups (VHSG) will be asked to record details of all births and neonatal deaths in their villages. The data collected will include:

1. Village name
2. Estimated Date of Delivery
3. Date of delivery
4. Gender
5. Prematurity
6. Place of delivery
7. Birth weight
8. Alive at 28 days

The data will be brought to monthly VHSG meeting and entered in to a database by a member of the SBLT. Each VHSG will receive a \$2 phone credit card for each completed birth data collected. If a neonate dies, a verbal autopsy will be performed by one of the Saving Babies Lives team using the WHO Verbal autopsy tool [23].

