## **6.7. Inclusion Criteria**

- Work as a VHSG
- Live in a village served by a chosen HC
- Are able to commit to attend meetings regularly
- Give consent to participate in the meetings

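### The only stated route for birth and death records is the monthly VHSG meeting; the protocol leaves unclear whether control clusters hold it, and either answer compromises the mortality comparison

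*Protocol*

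**What the plan says.** The Perinatal Mortality part of section 3.2 makes the village workers the outcome recorders: they "will be asked to record details of all births and neonatal deaths in their villages". It gives one route from recorder to database: "The data will be brought to monthly VHSG meeting and entered in to a database by a member of the SBLT". It explains why active collection is needed: "often the births and deaths of young infants, particularly those born at home, are not registered". One list of data items and one phone-credit payment per completed birth record apply, with no distinction by arm.

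The meeting itself is described elsewhere. Section 3.2 lists "Establishment of baby health meetings for VHSGs" as the second of four study components. The VHSG Baby Health Meetings section says "Monthly meetings will take place at the HC in order for the group to discuss problems, attempt to arrive at solutions, and share learning", with the Saving Babies Lives team (SBLT) as facilitators.

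On where it is held, the protocol points two ways:
- **Confined.** Set-up: "The BHM will be conducted in the HCs chosen to be in the intervention group". Section 6.7 requires that a participant "Live in a village served by a chosen HC".
- **Everywhere.** The opening sentence of the Baby Health Meetings section places the meetings at each health centre. Section 7.7 has the team visit every health centre and invite every VHSG.

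**The concern.** A cluster trial can compare mortality between arms only if deaths are found equally well in both. Here the hand-over of outcome records is tied to an event that is also part of the intervention. The protocol itself says that young-infant births and deaths often go unregistered, so how many are found is likely to depend on how regularly the recorder meets someone who collects the form.

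The outcome matters. A one-third reduction in perinatal mortality is the secondary objective in section 4, and perinatal mortality is the primary outcome of the mortality analysis in section 8.1. That analysis compares intervention with control clusters only, so control records supply one whole side of it. Deaths never recorded cannot be recovered at analysis; at best their number can be varied in a sensitivity analysis.

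**Working it through.** **Step 1. Is the data meeting the Baby Health Meeting?** The Perinatal Mortality text says monthly VHSG meeting and does not use the name Baby Health Meeting. The identification is an inference. It rests on the Baby Health Meeting being monthly, attended by VHSGs and facilitated by the team whose members enter the data, on the Synopsis calling the programme's own meetings VHSG meetings, and on no other monthly meeting being described.

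**Step 2. What follows from each reading?**

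| Reading | Sections | Control clusters |
|---|---|---|
| Meetings confined to intervention or chosen centres | Set-up; 6.7 | No stated hand-over route; ascertainment can differ by arm |
| Meetings at every centre | Opening of Baby Health Meetings section; 7.7 | Same route as intervention, but controls receive an intervention component |

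Neither reading leaves the comparison intact.

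**Step 3. How large could an ascertainment bias be?** The protocol states no capture rate, so there is no figure of its own to reproduce. Let d be the share of deaths captured and b the share of births captured in an arm. The observed mortality rate is the true rate × d/b, so

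observed ratio = true ratio × (d_int / d_con) ÷ (b_int / b_con).

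*Case A: deaths missed selectively, births captured equally.* The second bracket is 1. The section 4 target of a one-third reduction is read as a ratio of 2/3 = 0.667. The capture shares below are assumptions, shown in both directions.

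| Deaths captured, intervention / control | Capture ratio | True 0.667 appears as | True 1.00 appears as |
|---|---|---|---|
| 100% / 90% | 1.11 | 0.74 | 1.11 |
| 100% / 80% | 1.25 | 0.83 | 1.25 |
| 100% / 67% | 1.50 | 1.00 | 1.50 |
| 90% / 100% | 0.90 | 0.60 | 0.90 |
| 80% / 100% | 0.80 | 0.53 | 0.80 |
| 67% / 100% | 0.67 | 0.44 | 0.67 |

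For example, 0.667 × 1.50 = 1.00 hides the whole target effect, and 1.00 × 0.667 = 0.67 creates it.

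*Case B: whole birth records missed regardless of survival.* Then d = b within each arm, the two brackets cancel, and the observed ratio equals the true ratio. This case is plausible in part, because survival to 28 days is an item on the same record as the birth.

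**The case against.** The strongest defence is that the mortality section draws no line between arms. It covers the whole province, uses one data list and pays every VHSG the same amount per completed record. That payment works against under-reporting in control villages. The sentences placing the meetings at each centre and inviting all VHSGs can be read as giving both arms the same route. All of this stands, and it limits what can be claimed.

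A reader might infer that the meetings are certainly held only in intervention centres, and hence that deaths are ascertained differently by arm. The documents do not support that as a fact: they conflict on where the meetings take place. Under the confined reading they show that the control route is not described, not that capture was worse.

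A reader might also infer that the bias runs against the programme. Fuller capture in intervention clusters is the more plausible direction, but nothing in the protocol fixes it, and Case B shows that it may be absent.

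The defence does not clear the plan. If the meetings do run everywhere, the control arm receives a listed component of the intervention. If a separate routine meeting was meant, the protocol never describes it.

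**Conclusion.** The point holds as a conflict in the protocol that compromises the mortality comparison whichever way it is resolved: unequal ascertainment on one reading, contamination of controls on the other. It is more than a missing detail, because the protocol fixes the outcome route and ties it to the intervention.

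The direction and size of any bias are unknown. A capture ratio of 1.5 or 0.67 would be enough to hide or create the full one-third reduction, but only if deaths are missed selectively. Those ratios are illustrations and do not estimate what happens in this trial. The conclusion also assumes that the monthly VHSG meeting is the Baby Health Meeting, the only candidate the protocol offers.

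**What to change.** 1. Reconcile the Perinatal Mortality text, the opening and Set-up parts of the Baby Health Meetings section, section 6.7 and section 7.7, so that they state plainly which centres hold the meetings.
2. In the Perinatal Mortality text, separate data hand-over from the Baby Health Meetings. Specify the same monthly data-only collection at every intervention and control health centre, whether or not the VHSG attends a meeting. Keep the common data list and per-record payment already there.
3. Report completeness by arm beside the mortality result, for example captured facility births against health-centre delivery counts. Section 3.3 gives only a province-wide total of about 5,300 deliveries a year, so this depends on counts being available by centre. State that it does not check home births or home deaths.

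A common route does not remove the monthly discussion of neonatal problems with intervention VHSGs, which may still sharpen their reporting; the write-up should say so.

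The cost is protocol wording and one form collection a month at each control centre, where outcome data must be gathered anyway. If each of the 28 health centres is one cluster (an assumption), that is 28 − 4 pilot − 10 intervention = 14 centres.

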### **Economic Evaluation**

A detailed cost analysis will be carried out to estimate the added resources that are required for the SBLP as compared with standard care. These costs will be combined with estimates for the incremental cost of caring for children at AHC, and HCs if attendance is found to increase, and by modelling the subsequent survival benefits in terms of incremental disability adjusted life years averted. This will indicate whether the SBLP is as cost-effective as compared to the existing standard of care (control arm).

At the time of the newborn health questionnaire, the mother will be asked about any health seeking costs the family incurred for their infant in the first four weeks of life.

